8.4.1. Prior/Concomitant/Follow-up Medications

All prior, concomitant and follow-up medications will be summarized in frequency tabulations (subject counts and percentages) and by World Health Organization ATC first level and PT. Listings will also be provided for general medications and concomitant QT prolonging medications. All tables described in this section will be produced on safety population.

8.4.2. Prior/Concomitant/Follow-up Procedures

All prior, concomitant and follow-up procedures will be summarized in frequency tabulations (subject counts and percentages) and by SOC and PT. Listings will also be provided for general medications/procedures and concomitant QT prolonging medications. All tables described in this section will be produced on safety population.

8.4.3. Prior/Follow-up Anti-Cancer Therapies

This section includes both AML therapies and non- AML therapies. AML therapies include surgery, radiation, systemic or any other therapy for the subject's AML disease, particularly intensive AML chemotherapies as induction/re-induction/salvage chemotherapies, consolidation or maintenance therapies, HSCT, low-intensity AML therapies such as azacitidine, decitabine or LDAC, or other medications considered supportive care for AML, regardless of discontinuation

date of treatment. Non-AML therapies may consist of the same therapies like AML therapies but for other hematologic or non-hematologic malignancies.

All tables described in this section will be produced on both ITT and safety population.

Prior and follow-up therapies will be summarized separately in tables.

8.4.3.1. Anti-Cancer Procedures/Surgeries

A listing will be provided for procedure/surgery including indication and date of procedures/surgeries. All prior, concomitant and follow-up procedures will be summarized in frequency tabulations (subject counts and percentages) and by SOC and PT.

8.4.3.2. Radiations

The number and percentage of subjects who had any prior/follow-up radiation therapy will be presented by treatment group for the safety and ITT populations. Summaries will include total frequency of subjects receiving any prior/follow-up radiation therapy, as well as the frequency by type of radiation therapy received (i.e., external beam, radio-immuno therapy, brachytherapy, etc.) will be presented by treatment group and overall. For subjects with radiation therapy, treatment site, type of radiation therapy, location of external beam, start/stop date, dose, number of fraction, intent of therapy, and settings of therapy will be presented in a listing.

8.4.3.3. Systemic Anti-Cancer Medication for AML

The number and percentage of subjects with any prior/follow-up systemic anti-cancer medication for AML will be presented by treatment group and overall for ITT and safety populations. A similar summary will also be presented for medication for AML or Higher Risk MDS. A summary of the Follow-up AML therapies, and their associated responses will also be presented. For subjects with systemic anti-cancer therapy for AML, detailed information will be presented in a listing.

8.4.3.4. Systemic Anti-Cancer Medication Other than AML

The number and percentage of subjects with any prior/follow-up systemic anti-cancer therapy for diseases other than AML will be presented by treatment group and overall for ITT and safety populations. For subjects with systemic anti-cancer therapy, detailed information will be presented in a listing.

8.4.3.5. Stem Cell Transplants for AML

The number and percentage of subjects with any prior/follow-up stem cell transplants for AML will be presented by treatment group and overall for ITT and safety populations. For subjects with stem cell transplants, type, date of procedure, intent of therapy, and disease status at the time of HSCT will be presented in a listing.

8.4.4. Prior/Concomitant/Follow-up Transfusions

The number of subjects receiving any transfusion product, and the number of subjects receiving any transfusion of particular type (red blood cells, whole blood, platelets, plasma, other) will be

summarized by treatment groups. Prior /concomitant/follow-up transfusions will be summarized in separate tables for the safety population.

The number of subjects who are RBC transfusion dependent versus independent at baseline, the median transfusion burden at baseline, the changes from dependence to independence, independence remaining independent achieved at least 56 days RBC transfusion independence during treatment period together with the time to transfusion independence and duration of transfusion independence will be summarized by treatment groups.

The number of subjects who are platelet transfusion dependent versus independent at baseline, the median transfusion burden at baseline, the changes from dependence to independence, independence remaining independent achieved at least 56 days platelet transfusion independence during treatment period together with the time to transfusion independence and duration of transfusion independence will be summarized by treatment groups.

Transfusion type, number of units, reasons for taking transfusion, and dates of transfusions will be listed.

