### **7.2.1. AG-221 Treatment**

Subjects randomized to the AG-221 treatment arm will receive continuous 28-day cycles of AG-221 100 mg PO QD for 28 days. In addition, subjects may receive BSC per standard institutional practice and as deemed necessary by the investigator. In order to optimally benefit from the AG-221 treatment, the investigator should aim to treat subjects for at least 6 cycles or as long as subjects continue to benefit from the treatment until the End of Trial. Subjects may be discontinued from the treatment for any of the reasons detailed in Section 11.1.

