8.4. Prior/Concomitant/Follow-up Medications/Procedures/Therapies

Prior medications/procedures/transfusions are defined as medications/procedures/transfusions that were started prior to start of study treatment (start of study treatment refers to randomization date for BSC only group and first dose of study drug for other treatment groups) or have start dates missing. If start date is missing and end date is before start of study treatment medication will be classed as prior only.

Concomitant medications/procedures/transfusions are defined as non-study medications/procedures/transfusions that are started on or after the start of study treatment but before the end of the study treatment period or started before the start of the study treatment and ended or remain ongoing during the study treatment. For non-BSC groups, the end of the study treatment period is defined as the earlier date of last dose of study drug + 28 days and date of death. For BSC groups, the end of the study treatment period is defined as the earlier date of discontinuation from the treatment period and date of death.

Medication/procedure/transfusion with missing start date but end date on or after start of the study treatment (randomization date for BSC only group) and before the end of the study treatment period or with both missing start date and end date is also considered as concomitant medication/procedure/transfusion.

Follow-up medications/transfusions are defined as non-study medications/transfusions that are started after the date of the end of the study treatment period. All non-study medications and therapies will be coded by Anatomical Therapeutic Chemical (ATC) code and PT using the World Health Organization Drug Dictionary latest version. All procedures and surgeries will be coded by the Medical Dictionary for Regulatory Activities (MedDRA) latest version by system organ class (SOC) and preferred term (PT).

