11.1. Adverse Events

Adverse events will be analyzed in terms of treatment-emergent adverse events (TEAEs) which are defined as any AEs that begin or worsen on or after the start of study drug through 28 days after the last study treatment or until the EOT visit, whichever is longer, as well as those serious adverse events (SAEs) made known to the Investigator at any time thereafter that are suspected of being related to investigational product. All AEs will be coded using the Medical Dictionary for Regulatory Affairs® (MedDRA) version 22.0. The severity will be graded by the study personnel based on NCI National Cancer Institute Common Terminology Criteria for Adverse Events (CTCAE) Version 4.03.

A treatment-related TEAE is defined as TEAE that is suspected by the Investigator to be related to study treatment.

If a subject experiences the same AE more than once with different toxicity grade, then the event with the highest grade will be tabulated in “by grade” tables. If a subject experiences multiple AEs under the same preferred term (system organ class), then the subject will be counted only once for that preferred term (system organ class).

Summarizations of TEAEs per person-year of exposure are carried out in exposure-adjusted event rate, which is defined as number of events occurred in treatment exposure duration.

The number of subjects with at least one TEAE will be summarized. The incidence of TEAEs will be summarized by alphabetic order of SOC and descending order of PT for AG-221 group. Tables summarizing the incidence of TEAEs will be generated for each of the following:

- Summary of TEAEs;
- All TEAEs by SOC and PT;
- All TEAEs by decreasing frequency of PT for AG-221;
- All TEAEs per person-year of exposure, person-years of exposure is defined as (Sum of subjects’ overall treatment exposure (days) from first dose date (or randomization date for BSC only group) to the end of the TEAE period [c])/365.25;
- TEAEs related to study treatment;
- TEAEs by maximum severity;

- TEAEs with CTCAE grade ≥ 3 ;
- Related TEAEs with CTCAE grade ≥ 3 ;
- TEAEs with CTCAE grade ≥ 3 per person-years exposure;
- Related TEAEs with CTCAE grade ≥ 3 per person-years exposure;
- All AEs resulting in death;
- Serious TEAEs;
- Serious TEAEs per person-years exposure;
- All serious TEAEs by decreasing frequency of PT for AG-221;
- Serious TEAEs related to study treatment;
- Serious TEAEs related to study treatment per person-years exposure;

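### The concomitant transfusion table counts subjects with any transfusion over windows that differ by regimen, so it can overstate AG-221 transfusion use relative to CCR at an equal transfusion rate

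*SAP*

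**What the plan says.** SAP 8.4.4 summarizes by treatment group "The number of subjects receiving any transfusion product, and the number of subjects receiving any transfusion of particular type". It splits the output by period: "Prior /concomitant/follow-up transfusions will be summarized in separate tables for the safety population". Units, reasons and dates of individual transfusions appear only in a listing.

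SAP 8.4 sets the period boundaries. The on-treatment period starts at first dose, or at randomization for BSC only. "For non-BSC groups, the end of the study treatment period is defined as the earlier date of last dose of study drug + 28 days", or death if that comes first. "For BSC groups, the end of the study treatment period is defined as the earlier date of discontinuation from the treatment period", again or death.

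Dosing days per 28-day cycle (SAP 4.1) are 28 for AG-221, 7 for azacitidine, 10 for LDAC and 3 to 6 for IDAC. For AG-221, Protocol 7.2.1 adds that "the investigator should aim to treat subjects for at least 6 cycles". Protocol 7.2.2 to 7.2.5 state no such aim for the CCR options.

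Elsewhere the SAP does handle time. SAP 11.1 lists "All TEAEs per person-year of exposure", and SAP 8.2.1 (item 14) tabulates the number of transfusions and units in a fixed 56-day window before randomization. SAP 8.4.4 and 10.3.2.8 also summarize 56-day RBC and platelet transfusion independence. The HI-E criterion in SAP 15.6 includes an RBC transfusion reduction per 8 weeks.

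**The concern.** A count of subjects with at least one event rises with time observed. If one group is observed for longer, it shows a higher proportion even when its transfusion rate is the same. Here the window rule itself produces unequal lengths. The last AG-221 dose falls on day 28 of a completed cycle and the last dose of a CCR drug falls much earlier, so adding 28 days carries AG-221 further. BSC only gets no tail at all.

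At stake is how a descriptive safety table is read. Transfusions are among the safety assessments in SAP 4.2.4, and this is the table that sets on-treatment transfusion use side by side by group. As planned, a difference in it could reflect observation time, transfusion need, or both, and the table gives no means of separating them.

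**Working it through.** **Inputs from the documents.** Window rule: SAP 8.4. Dosing days: SAP 4.1. BSC-only cycle length of 28 days: SAP 5.1. The documents state no transfusion figure to reproduce. The nearest design figure is the OS assumption in SAP 4.4: 5.6/8 = 0.70 and 8/5.6 − 1 = 42.9%, as stated there.

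**Inputs assumed.** The documents give neither transfusion rates nor treatment duration by arm. I take the same constant rate λ in every group (0.5 to 4 transfusions per 28 days) and 1 to 6 completed cycles. I also assume no early death, and BSC-only discontinuation at the end of a cycle.

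**Step 1: window in days after k completed cycles.**
- Drug groups: 28(k − 1) + last dosing day + 28.
- AG-221: 28k + 28. Azacitidine: 28k + 7. LDAC: 28k + 10. IDAC: 28k + 3 to 28k + 6. BSC only: 28k.
- For k = 1: 56, 35, 38, 31–34 and 28 days. For k = 3: 112, 91, 94, 87–90 and 84 days.
- AG-221 minus the others, for any k: 21 (azacitidine), 18 (LDAC), 22–25 (IDAC) and 28 (BSC only).

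**Step 2: proportion with any transfusion.** P = 1 − exp(−λ × window/28). For AG-221 with k = 1 and λ = 0.5: 1 − exp(−0.5 × 56/28) = 1 − exp(−1) = 63.2%.

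| Cycles | λ per 28 days | AG-221 | Azacitidine | LDAC | IDAC | BSC only |
|---|---|---|---|---|---|---|
| 1 | 0.5 | 63.2% | 46.5% | 49.3% | 42.5–45.5% | 39.3% |
| 1 | 1 | 86.5% | 71.3% | 74.3% | 66.9–70.3% | 63.2% |
| 1 | 2 | 98.2% | 91.8% | 93.4% | 89.1–91.2% | 86.5% |
| 1 | 4 | 100.0% | 99.3% | 99.6% | 98.8–99.2% | 98.2% |
| 3 | 0.5 | 86.5% | 80.3% | 81.3% | 78.9–80.0% | 77.7% |
| 3 | 1 | 98.2% | 96.1% | 96.5% | 95.5–96.0% | 95.0% |
| 3 | 2 | 100.0% | 99.8% | 99.9% | 99.8% | 99.8% |
| 6 | 0.5 | 97.0% | 95.6% | 95.8% | 95.3–95.5% | 95.0% |

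CCR overall is a mixture of the last four columns, in proportions that the documents do not give.

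**Step 3: unequal treatment length, λ = 0.5.**
- AG-221 6 cycles, CCR 2 cycles: 97.0% against 67.5% (azacitidine) or 63.2% (BSC only).
- AG-221 3 cycles, CCR 6 cycles: 86.5% against 95.6% (azacitidine) or 95.0% (BSC only). The direction reverses.

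**Step 4: need varying strongly between subjects.** With gamma-distributed rates (shape 0.5), P = 1 − (1 + m/0.5)^(−0.5), where m is the mean count in the window. At 3 cycles each and a mean of 0.5 per 28 days, m = 2.0 for AG-221, giving 55.3%, against 51.5% (azacitidine) and 50.0% (BSC only). Over mean rates of 0.25 to 4 the gap against these two groups is about 2 to 6 points, so saturation is slower.

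**Step 5: does a rate remove the effect?** Expected events are λ × window/28. Dividing by window/28 returns λ. At λ = 1 and one cycle, AG-221 has 2.00 events over 2.00 units of 28 days, azacitidine 1.25 over 1.25 and BSC only 1.00 over 1.00. All give 1.0 per 28 days.

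**The case against.** The table is a descriptive summary in SAP Section 8, carries no test and sits outside the testing sequence in SAP 10.1. The drug groups share one written window rule. Transfusions after the window move to the follow-up table and are not lost. Treatment duration and number of cycles are tabulated by group (SAP 9.1), so a reader can see unequal exposure. Transfusion independence and HI-E are also reported. One completed cycle is the most favourable equal-cycle case for the argument: by six cycles at 0.5 per 28 days the gap is about 1 to 2 points. A subject who stops AG-221 on day 10 has the same 38-day window as one LDAC cycle. A bias in the direction described would count against AG-221, so it would not create a false efficacy claim.

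Most of this stands and limits the point to a minor one. It does not fill the gap. Exposure tables do not convert a crude count into a rate. The 56-day independence measure must be met during the treatment exposure period, so it also depends on how long that period lasts. HI-E is a responder threshold within a subject. None of these says how much transfusion each group received per unit of time on treatment.

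A reader might infer that AG-221 will show the higher proportion. The documents do not support that. The 6-cycle aim and the 8 against 5.6 month OS assumption point that way, but neither is a treatment duration, and Step 3 shows that the sign can change. A reader might also think that SAP Section 13 made this table an added outcome. Section 13 adds transfusion independence (SAP 10.3.2.8), not the count of subjects transfused.

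**Conclusion.** The point holds in conditional form. The concomitant table takes no account of time at risk, and its windows are 18 to 28 days longer for AG-221 at an equal number of completed cycles. At an equal rate it can therefore overstate AG-221 transfusion use relative to CCR. The effect is largest against BSC only, when treatment is short and when transfusion rates are moderate.

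Under a constant common rate, the one-cycle gap ranges from about 14 points (LDAC) to 24 points (BSC only) at 0.5 per 28 days. At three cycles it is about 5 to 9 points. It is under 2 points once the rate is 2 or more per 28 days and treatment lasts two or more cycles. These sizes rest on assumed rates and durations, completed cycles and no early death. Direction depends on realised treatment time. No endpoint test, type I error or power figure changes.

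**What to change.** In SAP 8.4.4:

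- **Rates.** Add RBC and platelet transfusion episodes and units per 28 days at risk, by treatment group, with numerator and denominator over the same period. For the drug groups, use first dose to the earliest of last dose + 28 days, death, subsequent AML therapy or data cut-off. For BSC only, use randomization to discontinuation + 28 days under the same limits. Protocol 6.3 and Table 3 (footnote u) already provide for collecting transfusions in follow-up until the first subsequent AML therapy.
- **A fixed horizon.** Add the cumulative incidence of first transfusion by Day 56 from first dose (randomization for BSC only), with death as a competing event. Count transfusions regardless of treatment discontinuation, and censor at subsequent AML therapy, when collection stops. This complements the rate, which fully removes the window effect only if need is constant over time.
- **The crude count.** Keep it as supplementary.

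The 28-day tail should stay in the rate. A window ending at last dose, which is how SAP 9.1 defines treatment end for the drug groups, would give one-cycle windows of 28, 7, 10 and 3–6 days. It would also drop the days after a chemotherapy course, and Protocol 7.2.2.1 itself links azacitidine with anemia and thrombocytopenia.

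Cost: a few extra table rows and some programming, from dates and units already collected.

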9. STUDY TREATMENTS AND EXTENT OF EXPOSURE

All analyses of treatment exposure will be conducted using the safety population. Only exposure to the AG-221, azacitidine, LDAC, and IDAC will be included in the treatment exposure summaries. Treatment exposure is not applicable to the BSC only treatment group. Duration of treatment and number of cycles will be calculated for all treatment groups, including the BSC only group.

Descriptive statistics for duration of treatment exposure, duration of treatment, average prescribed daily dose, average calculated daily dose, average daily dose, cumulative dose, dose intensity and relative dose intensity, will be presented by treatment groups. Individual subject listings will be provided to support the tables.

9.1. Duration of Treatment Exposure and Duration of Treatment

Duration of treatment exposure and duration of treatment will be summarized by treatment group.

Duration of treatment exposure (days) is defined as: Treatment end date – treatment start date + 28 days. The treatment start date is the date of the first dose of study drug, and the treatment end date is the last dose date. If death date or data cut-off is earlier than 28 days after treatment end date, duration of treatment exposure is defined as: the earlier of death date and data cut-off – treatment start date + 1. Duration of treatment exposure will be summarized by treatment group of AG-221, azacitidine, LDAC, and IDAC. For BSC only group, duration of treatment exposure is the same as duration of treatment defined below.

For AG-221, azacitidine, LDAC, and IDAC groups, duration of treatment (days) is defined as: Treatment end date – treatment start date + 1. For subjects who are still on treatment at a data cut-off date, treatment end date will be the earlier date of data cut-off and the last dose date.

For BSC only group, duration of treatment is defined as the period from date of randomization through the date of discontinuation from the treatment period, date of death, or clinical data cut-off date, whichever is earliest (calculated as the earliest of death, clinical data cut-off, or discontinuation date – randomization date + 1). Duration of treatment will be summarized for all treatment groups including the BSC only group.

See Section 5 for cycle length and cycle number calculations. Average cycle length (days), average number of days dosed per cycle, and number of treatment cycles will be summarized by treatment group. Average cycle length and average number of days dosed per cycle will not be summarized for BSC only group. The number of days dosed per cycle is defined as the number of days with a non-missing dosing date within that cycle. For average cycle length and average number of days dosed per cycle, a single average value will be computed for each subject first and then the descriptive statistics will be computed for each treatment group. Additionally, the count and percent of subjects by number of cycles of treatment will be provided for each treatment group.

Person-years of exposure will be calculated as duration of treatment exposure (days)/365.25 for all treatment groups except BSC only group. Person-years of exposure will be calculated as duration of treatment (days)/365.25 for the BSC only group.

9.2. Cumulative Dose

Cumulative dose will be calculated for AG-221, azacitidine, LDAC, and IDAC treatment groups. Cumulative dose is defined as the sum of all doses taken across the treatment period in mg.

Cumulative dose for AG-221 and LDAC = Sum of (administered dose of each visit in mg);

Cumulative dose for IDAC = Sum of (administered dose in g/m^2 of each visit).

Cumulative dose for azacitidine = Sum of (administered dose in mg/m^2 of each visit).

The dosage will be counted as zero for days when the study drug is not taken.

9.3. Dose Intensity

Dose intensity during the treatment is defined as the cumulative dose divided by the duration of treatment. Dose intensity will be calculated in the following way:

Dose intensity for AG-221 and LDAC = [cumulative dose in mg]/[duration of treatment];

Dose intensity for IDAC = [cumulative dose in g/m^2]/[duration of treatment].

Dose intensity for azacitidine = [cumulative dose in mg/m^2]/[duration of treatment].

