9.4. Relative Dose Intensity

Relative dose intensity is the dose intensity divided by the planned dose intensity.

For AG-221, the planned dose intensity is based on the assigned dose each time.

For LDAC, subjects randomized to LDAC treatment option will receive cytarabine 20 mg SC BID for the first 10 days of each every 28-day treatment cycle. Therefore, the planned dose intensity is 14.3 mg/day throughout the study;

For azacitidine, subjects in this group will receive 75 $\text{mg}/\text{m}^2/\text{day}$ for 7 days of each 28-day treatment cycle, so the planned dose intensity is 18.75 $\text{mg}/\text{m}^2/\text{day}$;

For IDAC, subjects randomized to IDAC treatment option will receive cytarabine 0.5 to 1.5 g/m^2 IV for the first 3 to 6 days of each 28-day treatment cycle. The dosing schedule is flexible with each site, so for calculation purpose, prior to the final analysis, the planned dose intensity for one specific cycle will be calculated in the following way:

Planned dose intensity = [dose administered (g/m^2) x actual duration (Days)]/28, which equals to X.X $\text{g}/\text{m}^2/\text{day}$.

Relative dose intensity for all four drugs mentioned above will be categorized into < 75%, 75% to < 90%, and $\geq 90\%$, and frequency counts will be provided by treatment group.

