9.7. Compliance

Overall and by cycle study medication compliance, which is measured by relative dose intensity (see Section 9.4 for details), will be summarised by treatment.

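### Relative dose intensity sets actual and planned dose on different time bases, inflating azacitidine and LDAC compliance, and the IDAC planned dose is built from the dose given

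*SAP*

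**What the plan says.** SAP Section 9.3 gives the actual rate: "Dose intensity during the treatment is defined as the cumulative dose divided by the duration of treatment". Section 9.1 supplies the denominator. The sentence beginning "For AG-221, azacitidine, LDAC, and IDAC groups, duration of treatment (days) is defined as" sets it at end date minus start date plus 1, and the same section says "the treatment end date is the last dose date".

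Section 9.4 divides that rate by a planned intensity:
- Azacitidine, 7 dosing days in 28: "so the planned dose intensity is 18.75" mg/m²/day.
- LDAC, 10 dosing days in 28: 14.3 mg/day.
- IDAC has no fixed constant because schedules differ by site. Instead "the planned dose intensity for one specific cycle will be calculated in the following way": dose administered "x actual duration (Days)]/28".

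The resulting RDI is reported in three categories (below 75%, 75% to below 90%, 90% or more). Section 9.7 makes it the adherence measure, overall and by cycle: "study medication compliance, which is measured by relative dose intensity".

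**The concern.** For azacitidine and LDAC, the planned rate counts the rest days of every cycle. The actual rate counts them for every cycle except the last. A subject who takes every dose therefore scores above 100%, and the excess is largest when cycles are few.

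For IDAC, the quantity called planned is the dose that was given, so the ratio does not compare delivery with intention.

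AG-221 is taken daily and has no rest days, so side-by-side tables overstate delivery of these comparators relative to AG-221. In an open-label trial, readers will ask whether control treatment was adequately delivered, and this is the table they will consult.

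**Working it through.** **Planned figures.** Azacitidine: 75 × 7 / 28 = 18.75 mg/m²/day. LDAC: 20 × 2 × 10 / 28 = 14.286, which rounds to 14.3 mg/day. Both SAP constants are correct.

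**Full dosing.** Take n on-schedule cycles with d consecutive dosing days each. The Section 9.1 duration is 28(n−1) + d, so RDI = 28n / [28(n−1) + d].

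| Cycles | Azacitidine (d = 7) | LDAC (d = 10) |
|---|---|---|
| 1 | 28/7 = 400% | 28/10 = 280% |
| 2 | 56/35 = 160% | 56/38 = 147% |
| 3 | 84/63 = 133% | 84/66 = 127% |
| 6 | 168/147 = 114% | 168/150 = 112% |

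(With the rounded 14.3, LDAC at one cycle is 279.7%.) AG-221, dosed on all 28 days, gives 100%.

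**Reduced dosing.** These patterns use reductions described in protocol Sections 7.2.2.1 and 7.2.3, only as illustrations. The comparison column uses the same data with the last cycle counted as 28 days. A 14-day delay makes Cycle 1 last 42 days.

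| Pattern | Cycles | As written | Last cycle = 28 days |
|---|---|---|---|
| Azacitidine 100% then 50%, one 14-day delay | 2 | 787.5/49/18.75 = 86% | 787.5/70/18.75 = 60% |
| Same | 3 | 1050/77/18.75 = 73% | 1050/98/18.75 = 57% |
| Azacitidine 100% then 50%, no delay (bicarbonate rule) | 2 | 787.5/35/18.75 = 120% | 787.5/56/18.75 = 75% |
| Same | 3 | 1050/63/18.75 = 89% | 1050/84/18.75 = 67% |
| LDAC 10 then 7 days, one 14-day delay | 2 | 680/49/14.286 = 97% | 680/70/14.286 = 68% |
| Same | 3 | 960/77/14.286 = 87% | 960/98/14.286 = 69% |
| Same | 9 | 2640/245/14.286 = 75.4% | 2640/266/14.286 = 69.5% |
| Same | 10 | 2920/273/14.286 = 74.9% | 2920/294/14.286 = 69.5% |

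The LDAC pattern is two categories too high at 2 cycles, one too high from 3 through 9, and right from 10. Azacitidine with the delay is in the wrong category at 2 cycles and the right one at 3. Without the delay it is wrong at both.

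**IDAC.** Read actual duration as dosing days d. For one cycle at daily dose D, the actual rate is D·d/d = D and the planned rate is D·d/28, so RDI = 28/d: 933% for 3 days and 467% for 6. If the actual rate is instead spread over 28 days, RDI is 100%. D cancels either way, so 0.5 and 1.5 g/m² score the same.

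**How common few cycles would be.** Assume the 5.6-month exponential median of SAP Section 4.4 holds for azacitidine and LDAC subjects. Deaths by day 28k are 1 − 2^(−(28k/30.4375)/5.6): 10.8%, 20.4% and 28.9% for k = 1, 2, 3. Deaths alone would then leave at least 20% with no more than 2 cycles and 29% with no more than 3.

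**The case against.** - **400% is a ceiling.** Protocol Section 7.2.2 lets sites skip weekends and still give all seven azacitidine doses. Seven doses over nine days give 28/9 = 311% at one cycle and 112.8% at six. Delays also lower the score. This stands as a qualification, but the bias remains.
- **The delayed azacitidine example is not general.** For subjects with reduced baseline counts, Section 7.2.2.1 ties 50% to recovery beyond 21 days. With a 22-day delay, two cycles score 787.5/57/18.75 = 73.7%, the same category as the 53.8% on a full last cycle. The example does fit the creatinine/BUN rule, and the 14-day boundary for subjects without reduced counts.
- **The LDAC example is narrow.** The 7-day course needs prolonged Grade 4 cytopenia with a Grade 4 infection or clinically significant bleeding, and persistence to nine cycles assumes a single delay. It is permitted, but its frequency is unknown.
- **By-cycle RDI is not shown to be wrong.** No by-cycle denominator is given, and SAP Section 15.1.2 leaves the cycle algorithm to dataset specifications. This stands: by-cycle RDI is under-specified.
- **The IDAC formula is an acknowledged workaround.** Its actual duration is undefined, and how cycles combine is unstated. Site flexibility explains the lack of a constant, but not the use of the administered dose as the plan.
- **The tables are descriptive.** Fully dosed subjects land in the right category, values above 100% are visibly odd, and days dosed (9.1), average daily dose (9.5) and dose modifications (9.6) partly show under-dosing. All true, and this limits the priority. It does not make the stated compliance measure correct.

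**Conclusion.** The concern holds. Followed exactly, the SAP gives overall RDI that is too high for azacitidine and LDAC, by the factor 28n/[28(n−1)+d] for on-schedule consecutive dosing, and nothing elsewhere in the SAP corrects it. For fully dosed subjects the summary values are wrong but the category is right. For under-dosed subjects with few cycles the category can be wrong as well. IDAC RDI carries no information on dose received against dose planned within a cycle, on either reading. The number of subjects affected cannot be computed, because cycles received are not given. The error is confined to descriptive exposure and compliance tables and should be corrected before they are produced.

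**What to change.** **Azacitidine and LDAC.** Define RDI as cumulative dose / [planned daily intensity × summed length of completed SAP Section 5.1 cycles + planned dose of the last started cycle]. The last cycle's planned dose is the full cycle dose, unless death or data cut-off falls inside that cycle; then count only doses due by that date. Checks:
- Delayed two-cycle azacitidine example: 787.5/(18.75 × 42 + 525) = 60%.
- Fully compliant azacitidine subject dying on Day 4 of Cycle 1: 300/300 = 100%, against 57% with an untruncated 28-day cycle.
- The same on Day 4 of Cycle 2: 825/(18.75 × 28 + 300) = 100%, against 138% as written and 79% untruncated.

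Use the same cycle lengths and rule for by-cycle RDI. State how due doses are counted when weekends are skipped. Footnote how stopping partway through the last cycle for other reasons is counted, and that AG-221 ends at last dose: an azacitidine subject stopping after Day 4 of Cycle 1 scores 300/525 = 57%, while a fully dosed AG-221 subject stopping then scores 100%. Leave AG-221 unchanged.

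Do not substitute the Section 9.1 duration of treatment exposure. It scores one fully dosed azacitidine cycle at 525/34/18.75 = 82%.

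**IDAC.** Use the same time base. Define planned intensity as prescribed daily dose × intended days at cycle start / 28, and state how cycles combine. Section 9 already lists "average prescribed daily dose", and Section 9.5 gives its IDAC units, so only intended days may need confirming with sites. Where these were not recorded, report prescribed against administered daily dose and days dosed instead of RDI.

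**Cost.** SAP text and derivation code, plus possible site queries on intended IDAC days. No dose or clinical rule changes.
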